2. STUDY OBJECTIVES, ENDPOINTS AND HYPOTHESES

2.1. Objectives

Primary Objective: The primary objective of this study is to estimate the incidence rate (percentage) of eyes with clinically significant slit-lamp findings (Grade 3 or 4) related to the study lens after approximately 2-weeks of lens wear.

Exploratory Objectives: The other objectives are to measure commitment to lens wear in neophyte subjects after approximately two weeks of wearing experience, measure Insertion & Removal (I&R) skills, evaluate new wearer confidence and motivation for lens wear, and assess lens performance (CLUE vision, comfort & handling scores).

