1.32	Continuance	For the subject to continue in the study, they must meet all three of the following criteria: • Visual acuity is 20/30 or better OD and OS. • The lens fit is acceptable OD and OS. • Investigator approval.

04-	Visit 1: Treatment 1 Lens Fitting			
Step	Procedure	Details If the Investigator does not approve the dispensing of the first study lens, then the study is terminated for that subject.		
1.33	Dispense	that subject. The lenses will be dispensed for a 6-8 day wearing period. Subjects will be encouraged to wear the study lenses every day, building up the wearing time if necessary. The lenses will be worn in a daily wear, daily disposable modality. Rewetting drops are permitted if needed. The subject should only use the sponsor supplied lens care products. (Section 6.1) Supply the subject a bottle of contact lens solution or saline for rinsing purposes, if necessary. Instruct subjects to return any unworn lenses to the clinical site. Subjects will be scheduled for their 1-week follow-up visit, ensuring that they wear the study lens to the follow-up visit. Note: Dispense the subject enough lenses to last them to their next scheduled visit, plus an extra pair. If the subject requires additional replacement lenses, instruct them to contact the clinical site for replacement. As much as reasonably possible, any damaged lens and packaging should be returned to the clinical site (wet, if possible) and then returned to the Sponsor. If lens damage is present, complete the Product Quality Complaint Form. If the PQC is due to foreign matter in the packaging, to the extent possible, this foreign matter must also be returned. The lens will be stored in labeled vial with saline, and clearly differentiated from the other worn lenses that will be shipped back to the Sponsor.		
1.34	Schedule next visit	The subject may continue to wear their habitual correction (spectacles) when not wearing study contact lenses. Schedule the follow-up visit to occur in 7 ± 1 days (counting the day of this visit as day 0, the subject may return on day 6 through 8). Ensure the subject is instructed to wear the study lenses to the follow-up visit. Remind the subject to bring their spectacle		

VISIT 2

The subjects must present to Visit 2 wearing the study lenses. If the subject wishes to stop wearing contact lenses (discontinue), proceed to the Final evaluation.

		Visit 2: Treatment 1 Follow-Up 1	- 39
Step	Procedure	Details	

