2.19	Dispense	The lenses will be dispensed for a 6-8 day wearing period. Subjects will be encouraged to continue to wear the study lenses every day. The lenses will be worn in a daily wear, daily disposable modality. Rewetting drops are permitted if needed. The subject should only use the sponsor supplied lens care products. Instruct subjects to return any unworn lenses to the clinical site. Subjects will be scheduled for their 1-week follow-up visit, ensuring that they wear the study lens to the follow-up visit. Note: Dispense the subject enough lenses to last them to their next scheduled visit, plus an extra pair. If the subject requires additional replacement lenses, instruct them to contact the clinical site for replacement. As much as reasonably possible, any damaged lens and packaging should be returned to the clinical site (wet, if possible) and then returned to the Sponsor. If lens damage is present, complete the Product Quality Complaint Form. If the PQC is due to foreign matter in the packaging, to the extent possible, this foreign matter must also be returned. The lens will be stored in labeled vial with saline, and clearly differentiated from the other worn lenses that will be shipped back to the Sponsor. The subject may continue to wear their habitual correction (spectacles) when not wearing study
2.20	Schedule next visit	contact lenses. Schedule the follow-up visit to occur in 7 ± 1 days (counting the day of this visit as day 0, the subject may return on day 6 through 8). Ensure the subject is instructed to wear the study lenses to the follow-up visit. Remind the subject to bring their spectacle correction to the next visit (if applicable).

VISIT 3

The subjects must present to Visit 3 wearing the study lenses. The subject must bring their habitual spectacles to this visit, if necessary. If the subject wishes to stop wearing contact lenses (discontinue), proceed to the Final evaluation.

	-	Visit 3: Treatment 1 Follow-Up 2	
Step	Procedure	Details	
3.1	Adverse Events and Concomitant Medications Review	Review any changes to the subject's medical history or concomitant medications from the previous study visit. Record any changes, and any adverse events.	
3.2	Wearing Time	Record the average wearing time and comfortable wearing time.	
3.3	Wear Compliance	Confirm the subjects wear schedule.	
3.4	Subject Reported Ocular Symptoms	Subjects will respond to a verbal open-ended symptoms questionnaire.	

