3.5	Confidence & Motivation	The subject will complete the Confidence & Motivation Questionnaire directly.	
3.6	Follow-Up Questionnaires	The subject will complete the Follow-Up Questionnaire directly.	
3.7	Entrance Visual Acuity	Record the distance Snellen visual acuity with the contact lenses (OD and OS) to the nearest letter. Subjects must read the smallest line until at least 50% of the letters are read incorrectly.	
3.8	Subjective Lens Fit Assessment	Evaluate overall lens fit acceptance (acceptable or unacceptable) based on centration, movement and other fitting characteristics. An unacceptable fit is deemed by one of the following criteria: Ilimbal exposure at primary gaze or with extreme eye movement. edge lift. excessive movement in primary and up gaze. insufficient movement in all three of the following conditions: primary gaze, up gaze, and push-up test. Note: if lens fit is unacceptable subject will be discontinued from the study.	
3.9	Wettability Characteristics	Record the white light lens wettability of both lenses.	
3.10	Surface Deposits	Record any front and back surface lens deposits.	
3.11	Lens Removal (timed)	While being timed, the subject will remove the study lenses, one at a time. Lenses will be temporarily stored in a contact lens case with preservative free saline. Removal: Using a stopwatch or a Timer App, observe the subject and record how long it takes them to remove each lens (one at a time). Total removal time OD	
		Total removal time OS Total removal time OU	

	Visit 3: Treatment 1 Follow-Up 2		
Step	Procedure	Details	
		Note: Removal time starts when the subject first attempts to remove the lens (at the approach step) and stops when the lens is successfully removed.	
3.12	Lens Insertion (timed)	While being timed, the subject will re-insert the study lenses on their own, one at a time. Insertion: Using a stopwatch or a Timer App, observe the subject and record how long it takes for them to insert each lens (one at a time). • Enter total insertion time OD • Enter total insertion time OS Total insertion time OU Note: • Insertion time starts when the subject first attempts to insert the lens (at the approach step) and stops when the lens is placed on eye. • You may ask the subject to let you know when the lens is in.	
3.13	Lens Removal	The subject or Investigator will remove the study lenses and discard them.	

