3.14	Slit Lamp Biomicroscopy	FDA Slit Lamp Classification Scale will be used to grade the findings. If the subject has a Grade 3 slit lamp finding, it will be recorded as an Adverse Event and the subject will be monitored as per the guidelines given in section 13. If the clearance of the fluorescein needs to be expedited, preservative-free rewetting drops may be instilled.	

FINAL EVALUATION

The final evaluation will ordinarily take place immediately following the last scheduled follow-up visit per the study protocol. It may also take place at any point the subject discontinues the study or is terminated from the study.

Final Evaluation			
Step	Procedure	Details	1/-
F.1	Commitment to Lens Wear Questionnaire	The subject will complete the commitment to lens wear Questionnaire directly.	
F.2	Final Exam Form	Indicate if the subject completed the study successfully. If subject discontinued from the study, indicate the reason.	
F.3	Exit Refraction	Perform bare-eye subjective spherocylindrical refraction with a phoropter and record the best-corrected distance visual acuity (OD and OS) to the nearest letter.	

	Final Evaluation		
Step	Procedure	Details	
		NOTE: This step is not necessary if the subject was exited due to screen failure.	
F.4	Exit Slit Lamp Biomicroscopy (for subjects that are discontinued early)	FDA Slit Lamp Classification Scale will be used to grade the findings. If the clearance of the fluorescein needs to be expedited, preservative-free rewetting drops or saline may be instilled. This step is not necessary if the subject was exited due to screen failure. NOTE: This step is not necessary if the subject was	
		exited due to screen failure, or if biomicroscopy was performed as part of the final follow-up visit procedures (i.e., immediately prior to the final evaluation).	

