8.2. Withdrawal/Discontinuation from the Study

A subject will be withdrawn from the study for any of the following reasons:

- Subject withdrawal of consent.
- Subject not compliant to protocol (e.g., subject wearing the lenses overnight).
- Subject lost to follow-up.
- Subject no longer meets eligibility criteria (e.g. the subject becomes pregnant).
- Subject develops significant or serious adverse events necessitating temporary or permanent discontinuation of study lens wear.
- Subjects who have experienced a Corneal Infiltrative Event (CIE).
- Subjects who have experienced a symptomatic ocular adverse event necessitating temporary or permanent discontinuation of study lenses.
- Investigator's clinical judgment regarding the subject safety reasons (that it is in the best interest of the subject to stop treatment).
- Subject not compliant with study lens wear schedule (e.g., subject doesn't wear study lenses at all between visits).

Subject not successfully dispensed due to lack of efficacy and safety including poor vision, poor comfort
or unacceptable fit.

For discontinued subjects, the Investigator will:

- Complete the current visit (scheduled or unscheduled).
- Complete the Final Evaluation, indicating the reason that the subject was discontinued from the study.
- Record the spherocylindrical refraction with best corrected distance visual acuity.
- Collect used test article(s) (worn or brought to the visit) from the subject and discard them, unless
 otherwise stated in section 7.2.
- Collect all unused test article(s) from the subject.
- Make arrangements for subject care, if needed, due to their study participation

Additional subjects may be enrolled if a subject discontinues from the study prematurely, at the Sponsor's discretion.

In cases where a subject is lost to follow-up, every possible effort must be made to contact the subject and determine the reason for discontinuation/withdrawal. The measures taken to follow up must be documented including two written attempts and a certified letter (or equivalent) as the final attempt.

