14.9. Procedure for Handling Missing Data and Drop-Outs

Missing or spurious values will not be imputed. The count of missing values will be included in the summary tables and listings.

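### The visit pages and section 8.2 conflict on whether an attending subject who wishes to stop completes the visit, so exploratory 1- and 2-week data may be lost selectively

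*Combined protocol and SAP*

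**What the plan says.** Section 7.2 expects subjects to arrive at both follow-up visits with their lenses in. It then gives the same routing instruction in the introduction to each visit: "If the subject wishes to stop wearing contact lenses (discontinue), proceed to the Final evaluation". In both places it stands before step 2.1 or 3.1.

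The Final Evaluation has four steps. At F.1, "The subject will complete the commitment to lens wear Questionnaire directly". F.2 is the exit form with the reason for discontinuation, F.3 is refraction, and F.4 is "Exit Slit Lamp Biomicroscopy (for subjects that are discontinued early").

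Section 8.2 lists what the investigator does for a discontinued subject. The first item is "Complete the current visit (scheduled or unscheduled"), and the Final Evaluation comes after it.

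The exploratory objectives in section 2.1 include to "evaluate new wearer confidence and motivation for lens wear, and assess lens performance". Section 14.7 analyses these endpoints in the ITT population at each timepoint. Section 14.9 states "Missing or spurious values will not be imputed", and adds that missing counts will be shown in tables and listings.

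**The concern.** Section 7.2 and section 8.2 give different orders for the same subject. Up to five sites, each with a target of about eight subjects, could follow different rules in good faith.

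The resulting gaps would not be random. The trigger for skipping is the wish to stop lens wear. Section 1.5 gives the main reasons for stopping as problems with vision, discomfort and handling, which are the three CLUE domains this study collects. Under the visit pages, a person who is at the clinic and dissatisfied supplies none of the scores that would show it. Means at 1 and 2 weeks would then lean towards satisfied wearers, in a study sized to learn about the new-wearer experience (section 14.2). Answers not collected at the visit cannot be recovered later.

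**Working it through.** **1. What each route collects.** Step numbers are from section 7.2.

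| Item | Visit 2 / Visit 3 step | Final Evaluation step |
|---|---|---|
| Adverse event review | 2.1 / 3.1 | none listed |
| Wearing time | 2.2 / 3.2 | none listed |
| Ocular symptoms | 2.4 / 3.4 | none listed |
| Confidence and motivation | 2.5 / 3.5 | none listed |
| Follow-Up Questionnaire | 2.6 / 3.6 | none listed |
| Timed removal | 2.11 / 3.11 | none listed |
| Timed insertion | 2.13 / 3.12 | none listed |
| Slit lamp | 2.12 / 3.14 | F.4 |
| Commitment | – | F.1 |
| Reason for discontinuation | – | F.2 |

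That the Follow-Up Questionnaire carries CLUE is an inference. Section 2.2 calls for CLUE at 1 and 2 weeks, and the only other self-completed questionnaire among the visit steps is Confidence & Motivation. The questionnaire pages of Appendix A are not visible.

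**2. The plan's own figures.** Sections 4.3 and 14.2 give about 40 enrolled and 30 completing. Implied non-completion is 1 − 30/40 = 25%. The figures agree with each other: 30/(1 − 0.25) = 40, and 5 sites × 8 = 40. The 25% is implied rather than stated. It covers all causes, and because enrolment is counted at consent it includes screen failures.

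**3. Shift in an observed mean.** Let f be the share whose score is missing because of the skip, and d the gap between the mean of those observed and the mean of those missing. The full mean is (1 − f) × observed mean + f × missing mean, so

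observed mean − full mean = f × d.

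The documents give neither f nor d; both are assumed here.

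| Skipped | f | d (CLUE points) | Shift |
|---|---|---|---|
| 2 of 40 | 0.05 | 5 | 0.25 |
| 4 of 40 | 0.10 | 20 | 2.0 |
| 10 of 40 | 0.25 | 10 | 2.5 |
| 10 of 40 | 0.25 | 20 | 5.0 |
| 10 of 40 | 0.25 | 30 | 7.5 |

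A gap of 20 is one SD on the scale in section 2.2. That section equates a 5-point rise in the mean with a 10% shift in the distribution. This checks: 5/20 = 0.25 SD, Φ(0.25) = 0.599, and 0.599 − 0.5 ≈ 0.10.

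**4. Why 10 of 40 is a ceiling.** If s of the 10 planned non-completers leave before Visit 2 (screen failure, unacceptable fit, unsuccessful training), then f is at most (10 − s)/(40 − s). With s = 0 this is 0.25. With s = 5 (assumed) it is 5/35 = 0.143, and a 20-point gap gives 0.143 × 20 = 2.9 points. This counts every skipped subject as a planned non-completer.

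**5. Under section 8.2.** An attending subject supplies the visit's data, so the skip adds no missing values at that visit. Someone who stops at Visit 2 has no 2-week data under either rule.

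**The case against.** The strongest reply is that section 8.2 already orders the visit to be finished, so the protocol read as a whole does not discard these data. That is right as far as it goes, and it makes this an unreconciled conflict rather than a settled design decision. It does not remove the problem, because the contrary sentence stands at the head of the pages that sites work from.

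Several stronger readings are tempting, and the documents do not support them:

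- **A reader might infer that 1- and 2-week results will come mainly from people who want to continue.** No figure says how many attending subjects would be skipped.
- **A reader might infer that anyone not committed to lenses bypasses Visit 3, so the two groups cannot be compared.** The routing applies to subjects who wish to stop in the sense of discontinuing. Commitment concerns wear after the study and is asked at F.1, normally straight after Visit 3. A subject can complete Visit 3 and then answer No.
- **A reader might infer that the primary endpoint is damaged.** F.4 keeps the slit lamp for early discontinuations.
- **A reader might infer that adverse events go unrecorded.** Section 13.3 requires every event during enrolment to be documented. Only the prompt within the visit is lost.
- **A reader might use a skipped share above 25%.** That exceeds the planned loss from all causes, and the same subjects cannot produce a recoverable loss at both visits.

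It is also fair to say that all affected endpoints are exploratory and descriptive, that missing counts will be visible, and that the main reason for stopping is still captured as a category. With 30 completers and SD 20, the standard error of a CLUE mean is 20/√30 ≈ 3.7 points, so a shift of 1 to 3 points lies within sampling noise. These points limit the importance of the issue. They do not settle which instruction applies, and a bare missing count does not separate those who attended and were skipped from those who never came.

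**Conclusion.** The point holds as a contradiction between the introductions to Visits 2 and 3 in section 7.2 and the list for discontinued subjects in section 8.2. Where the visit pages are followed, patient-reported and timed measures are lost selectively from attending subjects who quit, and the exploratory 1- and 2-week summaries could be biased favourably. The size cannot be known from the documents. On assumed inputs it is about 2 CLUE points for 4 of 40 skipped and 5 points at the 10-of-40 ceiling, both with a 20-point gap. The favourable direction rests on the assumption that those who quit would score lower, which the cited reasons for stopping make plausible. The primary measurement, commitment and reason for discontinuation are not lost by this route. It should be corrected, but it does not threaten the main result.

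**What to change.** Reconcile the two visit introductions with section 8.2 as regards data collection. Suggested text for both: *A subject who attends and wishes to stop lens wear is asked, before the Final Evaluation, for this visit's adverse event review, wearing time, ocular symptoms, Confidence & Motivation Questionnaire and Follow-Up Questionnaire, and for timed removal and insertion if willing. Items declined are recorded as declined.* This uses only procedures already scheduled and leaves the rules on dispensing and stopping untouched.

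In sections 14.7 and 14.9, report missing counts at each visit by reason: left before the visit, did not attend, or attended but the item was not done. A split of results by commitment answer is optional, since the No group may be very small.

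The cost is one sentence in two places and a few extra table rows. The downside is some added visit time for a departing subject, who may decline.

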7.3. Unscheduled Visits

If, during the investigation, a subject requires an unscheduled visit to the clinical site, the following information will be collected, as appropriate:

- Chief complaint prompting the visit. If the reason is an adverse event, the applicable eCRF for the
 adverse event must be completed and subject record completed as appropriate.
- Date and time of the visit and all procedures completed at the unscheduled visit.
- Review of adverse event and concomitant medications.
- Documentation of any test article dispensed or collected from the subject, if applicable.
- Slit lamp findings (using the Slit Lamp Classification Scale).

If the Investigator withdraws a subject from the study, the final study visit case report forms must be completed indicating the reason(s) why the subject was withdrawn. The subject record must be completed documenting the date and primary reason for withdrawal and the study CRA notified.

Any ocular and non-ocular Adverse Events that are ongoing at the time of the study visit will be followed by the Investigator, within licensure, until they have resolved, returned to pre-treatment status, stabilized, or been satisfactorily explained. If further treatment i.e., beyond licensure is required, the subject will be referred to the appropriate health care provider.

The following information will be collected during an unscheduled visit.

	Unscheduled Visit			
Step	Procedure	Details		
U.1	Reason for unscheduled visit	Indicate if the only reason for the visit is that the subject requires additional test articles. If the reason is other than resupply of previously dispensed lenses, specify the reason for the visit.		
U.2	Chief Complaints (if applicable)	Record the subject's chief complaints for reasons for the unscheduled visit.		
U.3	Adverse Events and Concomitant Medications Review (if applicable)	Review any changes to the subject's medical history or concomitant medications from the previous study visit. Record any changes, and any adverse events.		
U.4	Entrance VA (if applicable)	Record the entrance distance visual acuity (OD, OS) to the nearest letter.		

	Unscheduled Visit		
Step	Procedure	Details	3-
U.5	Subjective Sphero- cylindrical Refraction (if applicable)	Perform bare-eye subjective spherocylindrical refraction with a phoropter (adopt the maximum plus to maximum visual acuity (MPMVA) approach and use the duo-chrome test for binocular balancing) and record the best corrected distance visual acuity to the nearest letter (OD, OS).	
U.6	Slit Lamp Biomicroscopy (if applicable)	FDA Slit Lamp Classification Scale will be used to grade the findings. If the clearance of the fluorescein needs to be expedited, preservative-free rewetting drops may be instilled.	
U.7	Dispensing (if applicable)	If the subject requires additional lenses to complete the wear period and is eligible to do so, provide additional lenses per the dispensing instructions given in the detailed study procedures.	
U.8	Exit Visual Acuity (if applicable)	Record the subject's exit distance visual acuity (OD, OS) to the nearest letter.	

NOTE: If the only reason for the unscheduled visit is that the subject requires additional test articles, only the dispensing information needs to be recorded.

